4.2.3. Sensitivity analyses

A sensitivity analysis to jointly assess BE across all doses will be performed on Part B using a statistical model incorporating all doses used in Part B if at least one dose fails to achieve BE in Part B.

Model Specification

 • $\log_e (\text{PK parameter}) = \beta_0 + S_i + \beta_1 * \log(\text{dose}) + \beta_2 * F + \beta_3 * F * \log(\text{dose}) + \epsilon_j$ 
 ○ β_0 is the Intercept of reference; β_1 is the main effect for dose for reference (slope); β_2 is the difference of intercept between the two formulations; β_3 is the difference of slope between the two formulations ○ Dose: 1, 2, 4, 6, or 8 mg; F: manufacturing process (process 1 or process 2) ○ S_i is the random effect for subject I; ϵ_j is the random error • Model based comparison for each dose 
 ○ For each dose, a contrast statement will provide the estimate and 90% CI, these will be used to evaluate BE: 
 ■ The 90% CIs of the ratios of the geometric means for $AUC(0-t)$ and C_{max} (μ Process 2 / μ Process 1) are within the range of 0.80 - 1.25. ○ This model will incorporate all 5 doses within one model
Model Checking & Diagnostics

 • In case there is a problem with model convergence, the arithmetic means for loge-transformed $AUC(0-t)$ and C_{max} and the treatment differences within each subject will be calculated using only data from the subjects who have completed all periods. The mean treatment difference and paired-t test based 90% CIs for treatment difference in loge scale will be estimated. The results will be provided in an exponentially back-transformed scale.
Model Results Presentation

 • The estimates of the geometric means ratio between Process 1 and 2 (Part B) will be presented along with the associated 90% CIs and %CVw.

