2.1. Study Rationale

Daprodustat tablets manufactured via Process 1 have been administered in the daprodustat Phase III program and with the intent to be commercialized. Daprodustat tablets produced by a second process (Process 2) are being developed to enable manufacturing flexibility and add supply capacity.

To support the development of daprodustat tablets via Process 2, the proposed study, Study 213022, will be conducted and will consist of two parts, Part A and Part B. Part A and Part B will be conducted independently. Results from Part A will not be required prior to the start of Part B.

Part A will be a three-treatment period, period balanced crossover design to characterize the pharmacokinetic (PK) profile of 4 mg reference tablet made by Process 1 compared to two sets of 4 mg tablets made by Process 2 each with successively differentiated dissolution profiles. PK results from Part A will be used to justify how much variation in dissolution profiles may be acceptable and to establish the clinical relevance of dissolution profiles in order to obtain regulatory flexibility in the dissolution specification.

Part B will be a two-treatment period, period balanced crossover design to assess the PK bioequivalence (BE) of tablets produced by Process 1 and Process 2 following

administration of a single dose of 1 mg, 2 mg, 4 mg, 6 mg, and 8 mg of daprodustat in 5 groups of healthy participants. The purpose of Part B is to demonstrate BE for each of the dose strengths. The results from Part B will be used to support global file and supplying Japan with daprodustat manufactured by the new process.

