- For the 2 mg dose strength, eligible participants will be enrolled in the study and randomized in a 1:1 ratio to a treatment sequence of either Regimen F or G:

Regimen	Period 1	Period 2
F	Daprodustat 2 mg Process 2	Daprodustat 2 mg Process 1
G	Daprodustat 2 mg Process 1	Daprodustat 2 mg Process 2

- For the 4 mg dose strength, eligible participants will be enrolled in the study and randomized in a 1:1 ratio to a treatment sequence of either Regimen H or I:

Regimen	Period 1	Period 2
H	Daprodustat 4 mg Process 2	Daprodustat 4 mg Process 1
I	Daprodustat 4 mg Process 1	Daprodustat 4 mg Process 2

- For the 6 mg dose strength, eligible participants will be enrolled in the study and randomized in a 1:1 ratio to a treatment sequence of either Regimen J or K:

Regimen	Period 1	Period 2
J	Daprodustat 6 mg Process 2	Daprodustat 6 mg Process 1
K	Daprodustat 6 mg Process 1	Daprodustat 6 mg Process 2

- For the 8 mg dose strength, eligible participants will be enrolled in the study and randomized in a 1:1 ratio to a treatment sequence of either Regimen L or M:

Regimen	Period 1	Period 2
L	Daprodustat 8 mg Process 2	Daprodustat 8 mg Process 1
M	Daprodustat 8 mg Process 1	Daprodustat 8 mg Process 2

The total study duration for each participant will be approximately 7 weeks (minimum) for Part B. All participants will receive study treatment according to the randomization schedule.

Daprodustat will be supplied as film coated tablets for oral administration containing 1, 2, 4, 6, or 8 mg of daprodustat. The doses, tablet size, and description are provided in [Table 1](#). Participants are to take the daprodustat tablet(s) daily with water, and these tablets can be taken without regard to food.

Table 1 Description of Daprodustat and Placebo Tablets

Tablet size	Dose	Description
7 mm	Daprodustat 1 mg, 2 mg, 4 mg	7.0 mm round, compound radius, white film coated tablets
9 mm	Daprodustat 6 mg and 8 mg	9.0 mm round, compound radius, white film coated tablets

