4.2.2. Main analytical approach

Endpoint / Variables
Part A: AUC (0-t) and C _{max} of daprodustat
Part B: AUC (0-t) and C _{max} of daprodustat
Model Specification
Part A: For Part A the following statistical analysis method will be used: The exposure [AUC(0-t) and C _{max}] of daprodustat will be assessed by using a mixed effect model as described below: $\text{log}_e (\text{PK parameter}) = \beta_0 + \gamma_i + \tau_j + \pi_k + \epsilon_{ijkl}$ where β_0 is the intercept, γ_i is the random participant effect for ith participant, τ_j is the tablet manufacturing effect (j = dissolution 1, dissolution 2, Process 1), π_k is the period effect (k = period 1, period 2, period 3), and ϵ_{ijkl} is the random error. The model parameters will be estimated using Restricted Maximum Likelihood with the Newton-Raphson algorithm. The Kenward-Roger degree of freedom approach will be used. Given the random effect for subject i, the random error is assumed to be independently distributed within the subject. Point estimates, $\log_e \mu$, for the model-based means of PK parameters on loge scale will be provided for dissolution 1, dissolution 2, and Process 1 and a point estimate of the mean difference between comparisons ($\log_e \mu$ dissolution 1, 2 - $\log_e \mu$ Process 1) will be constructed along with the associated 90% CIs using the residual variances. The point estimates, the point estimate of the mean difference, and the associated 90% CIs on loge scale will be exponentially back-transformed to obtain the model-based

geometric means (μ), and the ratio for AUC(0-t) and Cmax (μ dissolution 1/ μ Process 1 and μ dissolution 1/ μ Process 2) and the associated 90% CIs, respectively.

Within-subject variability (%CVw) for the PK parameters will be estimated using within-subject variance from the analysis model as follows:

$$\%CVw (\%) = [\exp(\sigma_w^2) - 1]^{1/2} \times 100$$

AUC(0-inf) will be analyzed in the same manner.

Part B:

For each tablet strength of daprodustat (1 mg, 2 mg, 4 mg, 6 mg, and 8 mg), the following statistical analysis method will be used (separate model for each dose strength):

The exposure (AUC(0-t) and Cmax) of daprodustat will be assessed by using a mixed effect model as described below:

$$\log_e (\text{PK parameter}) = \beta_0 + \gamma_i + \tau_j + \pi_k + \varepsilon_{ijkl}$$

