where β_0 is the intercept, γ_i is the random participant effect for i th participant, τ_j is the tablet manufacturing effect (j = Process 1 or Process 2), π_k is the period effect (k = period 1 or period 2), and ε_{ijkl} is the random error.

The model parameters will be estimated using Restricted Maximum Likelihood with the Newton-Raphson algorithm.

The Kenward-Roger degree of freedom approach will be used.

Given the random effect for subject i , the random error is assumed to be independently distributed within the subject.

Point estimates $\log_e \mu$, for the model-based means of PK parameters on loge scale will be provided for each tablet strength and a point estimate of the mean difference between processes ($\log_e \mu$ Process 2 - $\log_e \mu$ Process 1) will be constructed along with the associated 90% CIs using the residual variances. The point estimates, the point estimate of the mean difference, and the associated 90% CIs on loge scale will be exponentially back-transformed to obtain the model-based geometric means (μ), and the ratio for AUC(0-t) and Cmax (μ Process 2 / μ Process 1) and the associated 90% CIs, respectively.

Bioequivalence will be evaluated using the FDA BE guidelines, Criterion 1. It is noted that if Criterion 1 fails, the next step per Japan BE guidance is Criterion 2. However, the study design is based on Criterion 1 given its more stringent criteria

- Criterion 1:

The 90% CIs of the ratios of the geometric means for AUC(0-t) and Cmax (μ Process 2 / μ Process 1) are within the range of 0.80 - 1.25.

- Criterion 2

The ratio of the geometric means for AUC(0-t) and Cmax (μ Process 2 / μ Process 1) is within the range of 0.90 - 1.11.

Within-subject variability (%CVw) for the PK parameters will be estimated using within-subject variance from the analysis model as follows:

$$\%CVw (\%) = [\exp(\sigma_w^2) - 1]^{1/2} \times 100$$

AUC(0-t) will be analyzed in the same manner.

Model Checking & Diagnostics

- In case there is a problem with model convergence, the arithmetic means for loge-transformed AUC(0-t) and Cmax and the treatment differences within each subject will be calculated using only data from the subjects who have completed all periods. The mean treatment difference and paired-t test based 90% CIs for treatment difference in loge scale will be estimated. The results will be provided in an exponentially back-transformed scale.
- This will be done for both Part A and Part B.

Model Results Presentation

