- Results of Part A and Part B will be presented in the same manner, separately.
- The estimates of geometric means of PK parameters (AUC(0-t) and Cmax) will be presented for each dissolution profile and Process 1 (Part A) or for Process 1 and 2 for each tablet strength (Part B), respectively. The estimates of the geometric means ratio between each dissolution profile and Process 1 (Part A) or between Process 1 and 2 (Part B) will be presented along with the associated 90% CIs and %CVw.
- AUC(0-t) will also be provided in the model results presentation, but the evaluation of the bioequivalence for Part B will not be done based on AUC(0-t).

Model Results Interpretation

Part A:

- There will be no formal statistical hypotheses for part A.

Part B:

- Bioequivalence will be determined if the 90% confidence interval (CI) of μ Process 2 / μ Process 1 falls within a range of 0.80 to 1.25. This is equivalent to carrying out two one-sided tests of hypothesis at the 5% level of significance.
- A demonstration of bioequivalence requires the null hypothesis for both AUC and Cmax to be rejected. All doses must meet the criteria for bioequivalence to be concluded.

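### SAP 4.2.3 says per-strength confidence intervals from an unchecked log-linear joint model evaluate BE after a strength has failed, and does not say that the result is supportive only (minor)

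*SAP*

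**What the plan says.** The Part B primary analysis in SAP 4.2.2 uses a "separate model for each dose strength". Each model has a random participant effect, a process effect and a period term, where π_k "is the period effect (k = period 1 or period 2"). BE requires the 90% CIs for AUC(0-t) and Cmax to lie within 0.80 to 1.25, and "All doses must meet the criteria for bioequivalence to be concluded". SAP 2.1 gives the independent enrolment and analysis of the strengths as its reason for making no Type I error adjustment.

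SAP 4.2.3 adds a joint model, run only if at least one strength has failed. It contains log(dose), process F and their product. β3 "is the difference of slope between the two formulations" and β2 is the difference of intercept. There is no period term. The use of the output is stated as "For each dose, a contrast statement will provide the estimate and 90% CI, these will be used to evaluate BE", with the same 0.80 to 1.25 limits. The only model check begins "In case there is a problem with model convergence". SAP 4.2.2 ends with a block on interpreting the results; 4.2.3 has none.

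Protocol 9.4.2 calls this an optional sensitivity analysis and leaves the details to the analysis plan. Protocol 2.1 gives the aim: "The purpose of Part B is to demonstrate BE for each of the dose strengths".

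**The concern.** In the joint model the log ratio at a given dose is β2 + β3·log(dose), so two parameters carry five ratios. An estimate for one strength is then built largely from the other four. If the true ratios do not lie on that line, a strength that is not bioequivalent can be pulled inside the limits.

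The analysis exists only after a failure, and 4.2.3 gives its intervals the same criterion and the same verb as the primary analysis. If a joint pass were counted, a failed strength could be declared bioequivalent mainly on data from other strengths. If it is not counted, the result can still mislead anyone who uses it to ask whether the failure was chance.

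**Working it through.** **Inputs from the documents** (SAP 4.2.2, 4.2.3 and 5): limits 0.80 and 1.25; 90% CI; 38 completers per strength, 19 per sequence; CVw 25% for Cmax and 19% for AUC; doses 1, 2, 4, 6 and 8 mg.

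**Assumptions, not from the documents:** the true ratios in each scenario, complete data, no true period effect, and the same CVw at every strength unless stated.

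**Step 1. Reproduce the plan's power.** σ² = ln(1 + 0.25²) = 0.0606. SE = √(2 × 0.0606/38) = 0.0565, on 36 df. With a true ratio of 1.0, exact two one-sided tests power is 97.4% for Cmax (plan: 97%) and 99.9% for AUC (plan: >99%). Treating the ten CIs as independent, (0.9742 × 0.9994)⁵ = 87.5% (plan: 87%). The plan's figures stand. The separate-model 90% CI is the point estimate divided and multiplied by exp(1.688 × 0.0565) = 1.100.

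**Step 2. Weights in the joint model.** With complete balanced data, the contrasts are the least-squares projection of the five mean log differences on (1, log dose), with 5 × 38 − 2 = 188 residual df. The share of each estimate that comes from that strength's own data is:

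| Strength | 1 mg | 2 mg | 4 mg | 6 mg | 8 mg |
|---|---|---|---|---|---|
| Own-data weight | 0.696 | 0.287 | 0.213 | 0.327 | 0.477 |
| CI factor, joint (separate 1.100) | 1.081 | 1.051 | 1.044 | 1.055 | 1.067 |

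The joint factors exclude any widening from lack of fit.

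Example: 4 mg truly at 1.25 and the rest at 1.00. The expected joint estimate at 4 mg is exp(0.213 × ln 1.25) = exp(0.213 × 0.2231) = 1.049. Its upper limit is then near 1.049 × 1.044 = 1.095, well inside 1.25.

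**Step 3. Pass rates** (Cmax, CVw 25%, 200,000 simulated trials per scenario, residual variance including lack of fit).

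One strength at 1.25, the others at 1.00:

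| Strength at 1.25 | 1 mg | 2 mg | 4 mg | 6 mg | 8 mg |
|---|---|---|---|---|---|
| That strength passes, separate | 5% | 5% | 5% | 5% | 5% |
| That strength passes, joint | 41% | >99.9% | 100% | 99.8% | 90% |
| All five pass jointly, given primary Cmax failure | 38% | 86% | 99% | 96% | 89% |

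Other patterns:

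- **6 and 8 mg at 1.25, the rest at 1.00.** The expected joint estimate is exp[(0.327 + 0.387) × 0.2231] = 1.173 at 6 mg and exp[(0.387 + 0.477) × 0.2231] = 1.213 at 8 mg. They pass jointly in 62% and 18% of trials. All five pass in 18%, against 0.2% separately.
- **1, 2 and 4 mg at 1.25, the rest at 1.00.** The 1 mg estimate is pushed outward, to exp[(0.696 + 0.407 + 0.118) × 0.2231] = 1.313. All five pass jointly in only 0.3%.
- **All five at 1.25, so the line is correct.** Each strength passes jointly in 5.0%.
- **All five at 1.00.** About 12% of trials fail the primary Cmax rule by chance, and the joint model passes all five in 98% of those.

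A joint pass therefore hardly separates chance failure (98%) from an isolated departure at 2 to 8 mg (86% to 99%). It does separate chance from the two step patterns (18% and 0.3%).

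**Step 4. Would a fit test be enough?** A lack-of-fit F test (3 and 180 df, 5% level) detects an isolated departure in 41% to 84% of trials and either step in 55%. It would help but cannot be relied on alone.

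**Step 5. A pooled model with strength as a category.** This model gives each strength its own ratio and pools only the residual variance. It holds about 5% if CVw is equal across strengths. With 1 mg at 1.25 and the others at 1.00, its false-pass rate at 1 mg is 7.4% when CVw is 26.8% at 1 mg and 22.6% elsewhere, and about 11% with 30% against 20%. The separate models stay at 5%.

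**The case against.** The best reply is that the plan already settles the matter. The trigger presupposes that BE has been judged for each strength before the joint model runs. The all-doses rule, the separate models and the independence rationale in SAP 2.1 all point to 4.2.2 as the sole basis for a conclusion. The section is titled as a sensitivity analysis, and the evaluation wording may mean only that the CIs are compared with the usual limits. Most of this stands. What remains is that 4.2.3 gives its CIs the task of evaluating BE and no passage states that they cannot change a conclusion.

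The scenarios are also assumed. A reader might take Protocol Table 1 as evidence for a step between 4 and 6 mg, because 6 and 8 mg are listed as "9.0 mm round, compound radius, white film coated tablets" and the lower strengths as 7 mm. The table gives diameters only. It says nothing about size altering the ratio between processes, so the step is an illustration.

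Nor is the line arbitrary. If exposure under each process followed a power model in dose, like the one SAP 5 uses to estimate CVw, a log ratio linear in log(dose) would follow. That is not evidence that Process 2 behaves so, and no check is planned.

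The missing period term matters little. It causes no bias with balanced sequences. An assumed 20/18 split at every strength, with a period effect of 0.1 to 0.2 on the log scale, shifts the ratios by 0.5% to 1.1%. Finally, the separate ratios and CIs are reported as well, so an informal comparison is possible.

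**Conclusion.** The point holds as a minor one. SAP 4.2.3 gives a decision-like role to per-strength CIs from a model whose linearity is neither supported nor checked, and leaves the standing of a joint pass to inference. Under the assumed ratios, a strength at the 1.25 limit passes jointly in 41% to 100% of trials when the departure is isolated. All five pass in 18% or 0.3% for the two steps, so the size depends heavily on the pattern assumed. If the line is right, there is no inflation.

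A reader might infer that the plan lets the sponsor rescue a failed strength, or that the Type I error of Part B is inflated. The documents do not support either. The primary analysis is untouched, its rules strongly imply that it governs, and the rates above become wrong BE conclusions only if a joint pass is counted.

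**What to change.** In SAP 4.2.3:

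1. Delete the clause that assigns the joint CIs to evaluating BE. State instead: *BE for each strength is decided only by the separate models in 4.2.2; the joint analysis is supportive and does not change any strength's BE conclusion.* This alone removes the risk of a wrong conclusion.
2. If the log-linear model is kept, add the period term and label the model exploratory. Show its ratios and CIs beside those from 4.2.2, with a lack-of-fit test, and note that a non-significant test does not establish the line.
3. A pooled model with strength as a category is optional, not a required replacement. If used, let the residual variance differ by strength, because the pooled version holds its level only when CVw is equal.

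The cost is a few sentences and one model statement, with no new data. The downside is that a joint pass can no longer rescue a strength that failed by chance. With all true ratios at 1.00, about 12% of trials fail the primary Cmax rule. The log-linear model would pass all five strengths in 98% of those, and the pooled categorical model in only 24%.

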4.3. Secondary [Endpoint(s)/Estimand(s)] Analyses

Part A

Objectives	Endpoints
Secondary	

 To assess remaining daprodustat pharmacokinetic parameters 	AUC (0-inf), Time of occurrence of Cmax (T_{max}), half life ($t_{1/2}$), clearance/fraction (CL/F) and volume/fraction (V/F) of daprodustat

Part B

Objectives	Endpoints
Secondary	

 To assess remaining daprodustat PK parameters 	AUC (0-inf), T_{max} , $t_{1/2}$, CL/F and V/F of daprodustat

4.3.1. Definition of endpoint(s)

Parameter	Parameter Description
AUC(0-inf) (h^*ng/mL)	The area under the concentration-time curve from zero time (pre-dose) extrapolated to infinite time (AUC(0-inf)) will be calculated as follows: $AUC(0-\infty) = AUC(0-t) + Ct / kel$
T_{max} (h)	The time to maximum observed plasma drug concentration following each dose will be obtained directly from the concentration-time data.
$t_{1/2}$ (h)	Terminal half-life will be calculated as follows: $t_{1/2} = \ln 2 / kel$
CL/F (mL/h)	Apparent clearance following oral dosing will be calculated as follows: $CL/F = Dose / AUC(0-\infty)$
Vz/F (mL)	Apparent volume of distribution after oral administration will be calculated as follows: $Vz/F = Dose / (kel \times AUC(0-\infty))$

NOTES:

- Additional parameters may be included as required.
- Kel is the terminal phase rate constant.
- Ct is the last observed quantifiable concentration.

4.3.2. Main analytical approach

The secondary endpoints of both Part A and Part B will be summary statistics of those PK parameters not summarized in the primary endpoint (AUC (0-inf), T_{max}, t_{1/2}, CL/F and V/F).

All pharmacokinetic endpoints will be summarized in tabular form. Descriptive statistics (n, arithmetic mean, standard deviation, minimum, median, maximum) will be calculated for all pharmacokinetic endpoints by regimen.

A participant listing of individual PK parameters for each treatment group will be provided. Pharmacokinetic parameters will be summarized by treatment group using descriptive statistics.

4.4. Safety Analyses

The safety analyses will be based on the Safety Analysis Set, unless otherwise specified.

Summaries will be provided separately for Part A and Part B.

4.4.1. Extent of Exposure

A listing of exposure will be created for both Part A and Part B. Summary tables of exposure will also be created.

4.4.2. Adverse Events

Adverse events analyses including the analysis of adverse events (AEs), Serious AEs (SAEs) and other significant AEs will be based on GSK Core Data Standards. An overview summary of AEs, including counts and percentages of participants with any AE, AEs related to study intervention, AEs leading to permanent discontinuation of study intervention, study intervention related AEs leading to permanent discontinuation of study intervention, SAEs related to study intervention, fatal SAEs, and fatal SAEs related to study intervention will be produced. Adverse events will be coded using the standard Medical Dictionary for Regulatory Affairs (MedDRA dictionary). A summary of number and percentage of participants with any adverse events by maximum severity will be produced. A separate summary will be provided for study intervention-related AEs. A study intervention-related AE is defined as an AE for which the investigator classifies the possible relationship to study intervention as “Yes”. A worst-case scenario approach will be taken to handle missing relatedness data, i.e. the summary table will include events with the relationship to study intervention as ‘Yes’ or missing. The summary table will be displayed by PT only. All SAEs will be tabulated based on the number and percentage of participants who experienced the event. Separate summaries will also be provided for study intervention-related SAEs. The summary tables will be displayed by PT and SOC. A study intervention-related SAE is defined as an SAE for which the investigator classifies the relationship to study intervention as “Yes”. A worst-case scenario approach will be taken to handle missing data, i.e. the summary table will include events with the

relationship to study intervention as 'Yes' or missing. **Adverse Events of Special Interest**

The following will be considered adverse events of special interest (AESI) for the purpose of analyses:

- Thrombosis and/or tissue ischemia secondary to excessive erythropoiesis
- Death, myocardial infarction (MI), stroke, heart failure, thromboembolic events, thrombosis of vascular access
- Cardiomyopathy

Pulmonary artery hypertension

- Cancer-related mortality and tumor progression and recurrence
- Esophageal and gastric erosions
- Proliferative retinopathy, macular edema, choroidal neovascularization
- Exacerbation of rheumatoid arthritis
- Worsening of hypertension

The summary of event characteristics will be provided for each AESI respectively, including number of participants with any event, number of events, number of participants with any event that is serious. The percentage will be calculated in two ways, one with number of participants with event as the denominator and the other with total number of participants as the denominator. The worst-case approach will be applied at participant level for the maximum grade, i.e. a participant will only be counted once as the worst case from all the events experienced by the participant. For action taken to an event, a participant will be counted once under each action.

Additional Safety Assessments

